2.2. Sample Size and Power Considerations

Percent change in TG is analyzed based on log (post/pre) transformation, allowing for a normal distribution of the data. Standard deviations (SD) of raw percent changes up to 13% are akin to moderate SD on the log scale (30-40%). For the statistical precision calculations, a log-scale SD of 0.5 was used based on available evinacumab phase 1 data and is assumed to be conservative. With N=10 patients, the 90% confidence interval (CI) for an estimated mean reduction in triglycerides of 40% is approximately 20% to 55%. With N=12, the CI is 22% to 54%. A sample size of 24 is considered adequate to analyze the percent change in TG in the 3 genetic cohorts. Assuming a 20% drop out rate, approximately 30 patients will be needed to assess TG. Additional patients (up to a maximum of approximately 50 patients) will be enrolled with the intent to explore the effect of evinacumab on development of pancreatitis.

For the FDG-PET uptake signal SUVmax, prior data on steroid-treated patients yielded a natural log-scale SD of change of 0.66 ([Shigekawa 2010](#)). This yields 80% power to yield a statistically significant ($\alpha=0.05$, 1-sided) change from baseline within the N=16 evinacumab-treated patients if the TRUE underlying geometric mean ratio (post/pre) is 0.65 (back-transformed from the log-scale; ~35% reduction). For comparison to the N=8 placebo-treated patients, assuming log-scale SD=0.15 for placebo based on reproducibility data, and 0.66 for evinacumab, there is 80% power if the TRUE underlying geometric mean ratio (GMR) of GMR's (evinacumab post/pre divided by placebo post/pre) is 0.64 (~36% reduction).

[figure not shown]
For the key MRI endpoint "mean f", which is the weighting coefficient between contrasting MRI regions (Klauss 2015), reported summary statistics yielded an SD estimate at most 5.96 for change from baseline. With this assumed SD, the N=24 patients with evinacumab post- and pre-values have 80% power to yield a statistically significant (alpha=0.05, 1-sided) change from baseline if the TRUE underlying mean change is 3.12 (~30% from baseline 10.5, which was observed by Klauss [Klauss 2015]). For the between-treatment comparison (N=16 evinacumab vs N=8 placebo), there is 80% power if the TRUE difference is 6.62 (~63% of the 10.5 baseline value observed by Klauss [Klauss 2015]).

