4.2.2. Secondary Endpoints

The secondary endpoints of the study are:

- Percent TG lowering from baseline following 2 to 24 weeks of repeated IV doses of evinacumab overall and subgroups with homozygous or compound heterozygous LOF mutations, heterozygous LOF mutations, and without LOF mutations in genes in the LPL pathway
- Changes in patient reported abdominal and GI symptoms, dietary habits, and symptom/dietary impact measures

- Degree of pancreatic injury/inflammation through ¹⁸F-FDG-PET imaging at baseline (placebo run-in) and change from baseline following 12 weeks of treatment with evinacumab as assessed by ¹⁸F-FDG standardized uptake values SUV_{max} and SUV_{mean}
- Degree of pancreatic injury/inflammation through DW-MRI at baseline (placebo run-in period) and the change from baseline following 12 and 24 weeks of treatment with evinacumab as assessed by ADC
- The total evinacumab concentrations, total ANGPTL3 concentrations, and ADA during the evinacumab treatment and follow-up periods
- Incidence and severity of treatment-emergent adverse event (TEAEs), SAEs, laboratory abnormalities, and other safety variables in patients treated with evinacumab

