10.4.3.2. Secondary and Exploratory Efficacy Analysis

Continuous secondary and exploratory endpoints will be analyzed similarly to the primary endpoint, except PP will not be computed. Binary endpoints will be summarized by counts and percents. Triglyceride mean percent change from baseline at each observation week will be summarized. Triglyceride mean percent change from baseline at each observation week will be analyzed and estimated for genetic mutations affecting LPL function (eg, homozygous LPL null [total LOF], heterozygous LPL null, with no LPL null gene mutations subgroups).

For the FDG-PET endpoint, comparisons will be within the evinacumab-treated patients in the double-blind period (week 12 vs week -2 for post/pre) and between the treatment groups in the double-blind period (week 12 vs week -2 for evinacumab in comparison to week 12 vs week -2 for placebo). In order to yield corresponding results, the MRI readout will be analyzed similarly as the FDG-PET endpoint. In addition, combining all evinacumab post/pre observations from the double-blind period (week 12 vs week -2) and the single-blind post/pre (week 24 vs week 12) for the patients who received placebo in the double-blind period, and post/pre (week 24 vs week -2 and week 24 vs week 12) for patients randomized to evinacumab during the double-blind period.

Summary statistics may be computed for time points beyond week 12 for the TG and continuous and exploratory endpoints in the patients randomized to evinacumab.

Summary statistics will be computed for the End of Day symptom diary and the symptom and dietary impact measure. These measures will also be psychometrically analyzed; this will be outlined in a separate psychometric analysis plan.

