5.7.4. Analysis of PET Variables

Descriptive statistical analyses for the PET variables defined in Section [4.7.4](#) will be summarized by treatment group and overall for the study, as well as by treatment group and overall within each cohort in the PET population.

For descriptive summaries, raw values, percent change, and/or when appropriate, absolute change from baseline will be provided for PET variables at each protocol scheduled time point (as defined by e-CRF visit label) for each treatment group. Missing values will not be imputed. For the evinacumab treated group, within-patient testing of endpoints with a non-normal distribution will use the Wilcoxon signed-rank test and endpoints with a normal distribution will use the paired t-test to evaluate the mean differences between baseline and each protocol visit. The p-value will be provided for descriptive purposes only

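### SAP 2.2 states power for between-arm PET and MRI comparisons and an N=24 MRI test that SAP 5.7.4 and 5.7.5 do not specify, and its MRI figures concern 'mean f', which is not a listed endpoint

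*SAP*

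**What the plan says.** **Power text.** SAP 2.2 repeats the imaging calculations of protocol 10.2. It gives 80% power, at one-sided alpha 0.05, for four analyses:

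- PET SUVmax within 16 evinacumab patients, true ratio 0.65.
- PET SUVmax between arms, 16 vs 8, ratio of ratios 0.64.
- MRI within patients, true change 3.12: "the N=24 patients with evinacumab post- and pre-values have 80% power to yield a statistically significant".
- MRI between arms: "For the between-treatment comparison (N=16 evinacumab vs N=8 placebo), there is 80% power if the TRUE difference is 6.62".

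The MRI variable is named in the same section: "For the key MRI endpoint 'mean f', which is the weighting coefficient between contrasting MRI regions".

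**Protocol analysis.** For FDG-PET, protocol 10.4.3.2 plans a comparison within evinacumab patients and one "between the treatment groups in the double-blind period (week 12 vs week -2 for evinacumab" against the same interval on placebo. For MRI, "the MRI readout will be analyzed similarly as the FDG-PET endpoint". It then describes combining evinacumab changes across periods, including "the single-blind post/pre (week 24 vs week 12) for the patients who received placebo in the double-blind period". That last sentence is incomplete and names no method.

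**SAP analysis.** SAP 5.7.4 (PET) and 5.7.5 (MRI) give descriptive summaries by treatment group and overall, plus one kind of test: "For the evinacumab treated group, within-patient testing of endpoints with a non-normal distribution will use the Wilcoxon signed-rank test", or a paired t-test if normal. The p-value is declared descriptive. SAP 4.7.5 sets the MRI baseline as the mean of two scans before the first double-blind dose, for both treatment periods.

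**Endpoints.** ADC is secondary: "Degree of pancreatic injury/inflammation through DW-MRI at baseline (placebo run-in period) and the change from baseline following 12 and 24 weeks". T2 and liver fat are exploratory (protocol 4.2.3). SAP 4.7.5 lists the same three. SUVmax and SUVmean are secondary.

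**The concern.** A reader of SAP 2.2 would conclude that between-arm and pooled imaging analyses are planned, and that the MRI power statements describe an endpoint of this trial. Neither follows from the analysis sections.

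The missing estimate matters because these are secondary endpoints in a randomised, placebo-controlled period. A within-evinacumab test cannot separate a drug effect from a 12-week change that would also have happened on placebo. Side-by-side summaries show the placebo values, but they do not give the difference between arms with its uncertainty.

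The SAP does not avoid between-arm estimates in general. SAP 5.11 plans a difference between groups with a 95% CI for the patient-reported outcomes.

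The departure is also unrecorded. SAP 1.2.4 item 5 cites protocol 10.4.3.2 but lists only SAP 5.7.2 and 5.9 to 5.12. The reason it gives is that an MMRM may not converge. That does not explain leaving out a two-group comparison of PET at one post-baseline visit.

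**Working it through.** **Step 1. Reproduce SAP 2.2.** Inputs from SAP 2.2: SUVmax log-scale SD 0.66 (evinacumab) and 0.15 (placebo); 'mean f' SD of change 5.96; one-sided alpha 0.05. Power is from the noncentral t distribution. For one sample, the noncentrality is change × √n / SD. For two samples, it is difference / SE.

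| Analysis | Noncentrality | Power |
|---|---|---|
| PET within, n=16, ratio 0.65 | 0.431 × 4 / 0.66 = 2.61 | 80.1% |
| PET between, 16 vs 8, ratio 0.64 (Welch, df 17.9) | 0.446 / 0.173 = 2.58 | 79.7% |
| MRI within, n=24, change 3.12 | 3.12 × √24 / 5.96 = 2.56 | 80.0% |
| MRI between, 16 vs 8, difference 6.62 (df 22) | 6.62 / [5.96 × √(1/16 + 1/8)] = 6.62 / 2.58 = 2.57 | 80.0% |

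All four stated figures reproduce.

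**Step 2. Match each powered analysis to a SAP method.**

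| Powered in SAP 2.2 | In protocol 10.4.3.2 | In SAP 5.7.4 / 5.7.5 |
|---|---|---|
| PET within evinacumab | Yes | Yes, nominal test (sidedness not stated) |
| PET between arms | Yes | No estimate, CI or test |
| MRI between arms | Yes, by reference to PET | No estimate, CI or test |
| MRI within, N=24 | Yes, incompletely worded | No evinacumab-aligned pooling |

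N=24 matches 16 evinacumab plus 8 placebo switchers. The protocol pairs a switcher's week 24 with week 12. SAP 4.7.5 instead keeps the pre-double-blind baseline in both periods, so a switcher's week-24 change would span 12 weeks on placebo and 12 on evinacumab. For TG, SAP 5.7.1 does move the switchers' baseline, to the mean of weeks 6, 8 and 12.

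**Step 3. Size of the unreported uncertainty (PET).** Take an observed between-arm SUVmax ratio of 0.64, SAP 2.2's SDs and unequal variances.

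- 16 vs 8: SE = √(0.66²/16 + 0.15²/8) = √(0.02723 + 0.00281) = 0.173; df 17.9; t = 1.735; half-width 0.301. 90% CI: 0.64 × exp(±0.301) = 0.47 to 0.86.
- 33 vs 17 (50 patients at 2:1, no dropout): SE = √(0.01320 + 0.00132) = 0.121; df 38.0; t = 1.686; half-width 0.203. 90% CI: 0.52 to 0.78.

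**Step 4. 'Mean f' without pooling.** Same method, SD 5.96, change 3.12, evinacumab arm only:

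| n | Basis | Power |
|---|---|---|
| 16 | arm size in SAP 2.2 | 64% |
| 26 | 33 × 0.8, the 20% dropout of SAP 2.2 | 83% |
| 33 | 50 × 2/3, no dropout | 90% |

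The evinacumab arm alone falls short of 24 only if enrolment stays near the 24-patient scenario.

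**Step 5. Listed MRI endpoints.** 'Mean f' appears only in protocol 10.2 and SAP 2.2. The documents give no SD of change in treated patients for ADC, T2 or liver fat, so no power can be stated for them.

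**The case against.** **The consequence is limited.** Protocol 10.1 plans no formal hypothesis testing, imaging p-values are descriptive, within-patient comparison is the declared design, and by-arm summaries will show the placebo data. All of this stands. It limits how serious the point is, but it does not supply the missing estimate.

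**The comparison may not have been abandoned.** SAP 1.2.4 item 5 deletes only the sentence about analysing continuous endpoints like the primary. It does not revoke the protocol's imaging comparison. A reader might infer that the sponsor decided to drop it, but the documents do not show that. They show an omission with no entry in the change table.

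**The MRI test is not simply underpowered.** A reader might take the 64% as the trial's MRI power. It holds only at 16 evinacumab patients, rises to 83% and 90% at the larger arm sizes, and concerns a variable that is not an endpoint.

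**N=24 might be reached another way.** SAP 3.8 covers both periods, and SAP 5.7.5 tests the evinacumab treated group at each visit. By week 24 all patients who continue have received evinacumab and have a run-in baseline. The text allows that reading, but it would mix 24 weeks of exposure with 12 and would count placebo time in the switchers' change. It is not the pairing in protocol 10.4.3.2.

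**The protocol need not contradict itself on baseline.** Protocol 4.2.2 (run-in baseline) and 10.4.3.2 (week 12 for switchers, introduced as an addition) can be read as complementary. The clear mismatch is SAP 4.7.5 against protocol 10.4.3.2.

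**Conclusion.** The point holds as a mismatch between the SAP's power section and its analysis sections. Three of the four imaging analyses powered in SAP 2.2 have no method in SAP 5.7.4 or 5.7.5: PET between arms, MRI between arms and MRI with N=24. The difference from protocol 10.4.3.2 is not recorded, and no power statement applies to any listed MRI endpoint.

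For SUVmax, the uncertainty left unreported is a 90% CI of 0.47 to 0.86 around 0.64 at 16 vs 8, or 0.52 to 0.78 at 33 vs 17. This assumes SAP 2.2's SDs of 0.66 and 0.15, taken respectively from steroid-treated patients and reproducibility data, and unequal variances. A common-variance model would give 0.42 to 0.96 and 0.49 to 0.84, so the variance assumption has to be stated.

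The point does not show an arithmetic error, a compromised decision rule or an inadequate sample size. Enrolment rests on TG precision and on exploring pancreatitis. The change should be made, but the primary result does not depend on it.

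**What to change.** 1. **Between-arm estimate.** Add to SAP 5.7.4 and 5.7.5 a descriptive week-12 evinacumab vs placebo estimate with CI, adjusted for baseline and allowing unequal variances by arm. Use a log-scale ratio for SUVmax and SUVmean, and a difference in change for ADC, following SAP 4.7.5. State the CI level: 90% matches the one-sided 0.05 of SAP 2.2, and 95% matches SAP 5.11. The protocol says only that comparisons will be made, so this form is a proposal. Add 5.7.4 and 5.7.5 to SAP 1.2.4 item 5.
2. **Pooled MRI analysis.** Either define it in SAP 5.7.5 with week 12 as the switchers' baseline and reconcile SAP 4.7.5 with protocol 10.4.3.2, or drop it, delete the N=24 figure and record this in SAP 1.2.4.
3. **'Mean f'.** In SAP 2.2 and protocol 10.2, stop calling it the key MRI endpoint and state that its power figures do not apply to ADC, T2 or liver fat. The 18% test/re-test value in protocol 8.2.4.2 should not be used to build replacement figures, because it is not an SD of change in treated patients.

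The cost is wording in both documents, entries in the SAP change table and a few extra descriptive tables. It needs no new data and no change in sample size.

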2.3. Study Plan

The study consists of a screening period of up to 37 days (which includes day -66 to day -59 [visit 1], day -58 to -52 [visit 1b], and day -51 to -39 [visit 2]), a placebo run-in period (day -28 to day -1), a 12-week double-blind treatment period (day 1 to day 85), a single-blind 12-week evinacumab treatment period (day 86 to day 169), and an off-treatment follow-up period (week 24 [day 170] to week 44 [day 309]).

A study flow diagram is in [Figure 1](#).

Figure 1: Study Flow Diagram

3. ANALYSIS POPULATIONS

In accordance with guidance from the International Conference of Harmonization of Technical Requirements for Registration of Pharmaceuticals for Human Use (ICH) guideline ICH E9 Statistical Principles for Clinical Trials (ICH, 1998), below are the patient populations defined for statistical analysis. The primary efficacy analysis population is the full analysis set (FAS) population. Additional patient populations are defined for safety, anti-drug (evinacumab) anti-body (ADA), pharmacokinetic (PK), total target (ANGPTL3), patient-reported outcomes (PRO), PET, MRI, biomarkers, and single-blind analyses. For the purposes of the definitions below, a patient is considered randomized to study treatment when they have been screened and received a double-blind treatment kit number allocated and recorded in the IVRS/IWRS database, regardless of whether the treatment kit was used or not.

As with all trials, odd cases (usually rare) occur for patient eligibility in the analysis populations. The following are three cases with the planned resolution of each type of case should they occur.

- Patients administered double-blind study treatment without randomization or before randomization will not be considered as “randomized” and therefore will not be included in any analysis population. The safety experience from these patients will be reported separately.
- For patients found to be randomized more than once in this trial, safety data from the first randomization will be included in the safety population, with safety data associated with the later randomization reported separately. Inclusion of efficacy data from the patient randomized more than once will be decided on a case-by-case basis prior to the unblinding of treatment assignments and documented in the study report.
- Patients successfully randomized and administered double-blind study treatment, but later found to violate inclusion/exclusion criteria, will be included in all analyses with appropriate documentation for the protocol deviation.

3.1. Full Analysis Set

The full analysis set (FAS) includes all randomized patients who receive any double-blind study drug; it is based on the treatment assigned (as randomized). Only observed data will be analyzed/summarized; no missing data will be imputed.

3.2. Double-Blind Safety Analysis Set

The double-blind safety analysis set (SAF) considered for safety analyses will be the randomized population who received at least 1 dose or part of a dose of double-blind study drug. Patients will be analyzed according to the treatment received (placebo or evinacumab). In addition:

- Randomized patients for whom it is unclear whether they took the study drug will be included in the safety population as randomized.
- For patients receiving study drug from more than 1 treatment group during the double-blind period, the treatment group allocation for as-treated analysis will be evinacumab.

3.3. Single-Blind Safety Analysis Set

The single-blind SAF considered for safety analyses will be the randomized population who received at least 1 dose or part of a dose of single-blind study drug.

3.4. Pharmacokinetic (PK) Analysis Set

The PK analysis set is defined as all randomized patients who received any study drug and have at least 1 non-missing measurement of evinacumab concentration following the first dose of the study drug. Treatment assignments for the DBTP are based on the treatment received (placebo or evinacumab).

The total target analysis set is defined as all randomized patients who received any study drug and have at least 1 non-missing measurement of total ANGPTL3 concentration following the first dose of study drug. Treatment assignments for the DBTP are based on the treatment received (placebo or evinacumab).

3.5. The Anti-evinacumab Antibody Analysis Set

The anti-evinacumab antibody (ADA) analysis set is defined as all randomized patients who received any study drug and have at least 1 non-missing ADA result following the first dose of study treatment. Treatment assignments for the DBTP are based on the treatment received (placebo or evinacumab).

3.6. Patient-Reported Outcomes (PRO) Analysis Set

The analyses of the PRO data in the respective treatment period (DBTP and SBTP) will be performed on all randomized patients who received any double-blind study treatment with a baseline and at least 1 non-missing post-baseline PRO evaluation. Treatment assignments for the DBTP are based on the treatment received (placebo or evinacumab).

3.7. PET Analysis Set

The analyses for PET will be performed on all randomized patients who received any double-blind study treatment with a baseline and a post-baseline PET evaluation. Treatment assignments are based on the treatment received (placebo or evinacumab).

3.8. MRI Analysis Set

The analyses for MRI in the respective treatment period (DBTP and SBTP) will be performed on all randomized patients who received any double-blind study treatment with a baseline and at least 1 post-baseline MRI evaluation. Treatment assignments for the DBTP are based on the treatment received (placebo or evinacumab).

4. ANALYSIS VARIABLES

4.1. Demographic and Baseline Characteristics

For each patient, demographic and baseline characteristics, except TG, will be obtained from the last available value up to the date of the first double-blind study treatment administration (i.e. baseline definition). Baseline TG is defined as the mean of the last 2 measurements during the placebo run-in (day -28, day -14) and week 0. For patients randomized and not treated in R1500-HTG-1522, the baseline value is defined as the last available measurement prior to the date of randomization.

All baseline safety and efficacy parameters (apart from those listed below) will be presented along with the summary statistics in the safety and efficacy sections.

The following variables will be summarized:

Demographic Characteristics

- Sex (Male, Female)
- Race (White, Black or African American, Asian, American Indian or Alaska Native, Native Hawaiian or other Pacific Islander, Not Reported, Other)
- Age in years (quantitative and qualitative variable: ≥ 18 to <45 , ≥ 45 to <65 , and ≥ 65)
- Ethnicity (Hispanic or Latino, Not Hispanic or Latino, Not reported, Unknown)

Baseline Characteristics

- Baseline Weight (kg)
- Baseline Height (cm)
- Baseline Body mass index (BMI) in kg/m^2 (quantitative and qualitative variable defined as <30 , ≥ 30)
- Smoking Status (never, former, and current smoker)
- Current alcohol consumption (yes/no)

Baseline Disease Characteristics

- Lipid parameters - quantitative variables for all efficacy parameters
- HbA1c both quantitative variable and qualitative variable defined as: $<5.7\%$, $\geq 5.7\%$ to $<6.5\%$, $\geq 6.5\%$
- Hs-CRP
- Lp(a): <30 , ≥ 30 to <50 , ≥ 50 mg/dL , and category ≥ 30 mg/dL (<75 , ≥ 75 to <125 , and ≥ 125 nmol/L , and category ≥ 75 nmol/L)
- Cohort assignment
- Patient genotype

4.2. Medical History

As applicable, patient medical history, pre-listed or not in the e-CRF will be dictionary coded by primary system organ class, high level term, and preferred term using the Medical Dictionary for Regulatory Activities (MedDRA), specifically the MedDRA version in effect at the time of the first database lock. The medical history of interest collected on dedicated and pre-listed e-CRFs is: cardiovascular history and risk factors, and pancreatitis history. Primary and secondary CVD prevention, CV risk factors categorized by high and very high risk are also defined below from pre-defined risk factors collected on e-CRF.

Medical history of interest is defined as the occurrence of these diseases:

1. Coronary heart disease (CHD)
2. CHD risk equivalents
3. Cardiovascular (CV) risk factors other than hypercholesterolemia (hypertension, type 2 diabetes, type 1 diabetes, family history of premature CHD).
4. Family history of type 2 diabetes

CHD and CHD risk equivalents will be derived from the respective e-CRF as follows:

1. Coronary heart disease (CHD) (regardless if it is ongoing or not) is defined as the occurrence of at least one of the following events:
 - Acute myocardial infarction
 - Silent myocardial infarction
 - Angina (chronic stable or unstable)
 - Coronary revascularization procedure (e.g. PCI, CABG)
2. CHD risk equivalent (regardless if it is ongoing or not) is defined as the occurrence of at least one of the following events:
 - Peripheral arterial disease (PAD)
 - Ischemic stroke
 - Chronic kidney disease (CKD)
 - Known history of diabetes mellitus (type 1 or 2) AND 2 or more additional risk factors among:
 - History of ankle-brachial index ≤ 0.90
 - History of hypertension
 - History of microalbuminuria or macroalbuminuria
 - History of proliferative diabetic retinopathy
 - Known family history of premature CHD

Secondary CVD prevention is defined as patients with any of the following history of CVD (other patients will be classified as primary CVD prevention):

- History of CHD (as defined above)
- History of ischemic stroke
- History of PAD with severity criteria defined as one of the following events:
 - PAD and ankle brachial index ≤ 0.90
 - Peripheral revascularization procedure (angioplasty, stenting) for PAD
 - Thrombolysis for PAD
 - Peripheral revascularization surgery (arterial bypass) for PAD

CV Risk Factors are defined for this study as high risk and very high risk below.

- Very high CV risk patients are defined as patients with CHD or CHD risk equivalents.
- High CV risk patients are defined as all other patients.

